12.0 SUBJECT ELIGIBILITY CRITERIA

12.1 Inclusion Criteria

- 1) Male or female
- 2) Any age
- 3) Presenting to CUH Emergency Department
- 4) Symptomatic of respiratory tract infection as evidenced clinically by the presence of any of the following indicators:
- Acute onset persistent cough (with or without sputum)
- Hoarseness
- Nasal discharge or congestion
- · Shortness of breath
- Sore throat
- Wheezing
- Sneezing
- Persistent Acute respiratory distress syndrome
- Influenza like illness
- Fever ≥ 37.8°C
- Any other symptom known to be indicative of acute respiratory episode such as palpitations, headache, anosmia (COVID) or gastrointestinal symptoms (diarrhoea) (influenza)
- 5) Signed consent form for participation
- 6) Requiring standard of care diagnostic testing as per CUH Trust IPC policy
- 7) Able to read and/or understand the age-appropriate participant information sheet in English.

12.2 Exclusion Criteria

- 1) Unwilling or unable to comply with study nasopharyngeal swabbing procedures
- 2) Those who are incapacitated or deemed to be lacking capacity to provide informed consent to participate
- 3) Prisoners or young offenders.

13.0 STUDY PROCEDURES

13.1 Patient Screening and Recruitment

The Investigator, Research Nurse or designated member of the research team will identify potential participants who present at the Emergency Department with suspected acute respiratory tract infection. The potential participant will be screened against the inclusion/exclusion criteria to determine their suitability for recruitment into the study. Potential participants will be provided with a copy of the patient information sheet for the study (as appropriate for their age group) and given as much time as they require to ask any questions and consider whether they want to take part or not. Following the informed consent process and signing of the consent form, the participant will be considered to have been recruited and enrolled into the study and will be allocated a 3-digit study identification number.

13.2 Informed Consent Process

As the study includes participants of all ages, it is vital that an age-appropriate Participant Information Sheet (PIS) is given to the participant and/or parent/legal representative from the following categories:

- 1) Adults aged 16 years and above
- 2) Children aged 11 to 15 years of age
- 3) Children aged 5 to 10 years of age
- 4) Parent/legal guardian of children 15 years of age or below.

All versions of the PIS and corresponding Informed Consent/Assent Forms must be prospectively approved by the Research Ethics Committee (REC) in line with Good Clinical Practice (GCP), local regulatory and legal requirements. The Investigator or designee must ensure that each study participant, and/or parent/legal guardian if the participant is aged 15 years or less, is fully informed about the nature and objectives of the study and possible risks associated with their participation.

The Investigator or designee will obtain written informed consent from each participant aged 7 years and above, and/or the parent/legal guardian if the participant is aged 15 years or below, before any study-specific activity is performed. The Investigator will retain all original signed consent forms in the Investigator Site File. Each participant will be given a photocopy of their own signed consent form, and a scanned copy will be added to each participant's electronic patient medical record.

If any new information about the Logicore System becomes available during the course of recruitment into the study, which might affect the participant's willingness to continue participating in the study, it will be communicated to the participant and/or their parent/legal guardian as soon as possible. As participants are only involved with the study during one visit to the ED, it is unlikely this information will affect those who have already been recruited into the study. However, if it is deemed appropriate, depending on the nature of the new information, this will be communicated to previous participants verbally via the telephone or by written follow up letter if necessary. Potential new participants will be informed of the new information during the informed consent process, so they are fully appraised of the most up-to-date details. The patient information sheets would be amended accordingly and submitted to the REC for review and approval as quickly as possible.

13.3 Withdrawal of Consent

Participants may withdraw from the study at any time at their own request, (or at the request of the parent/legal guardian if the participant is aged 15 years or less) without providing a reason and without any prejudice as to their further medical care and treatment. Similarly, participants may be withdrawn from the study at any time at the discretion of the Investigator or Sponsor for safety, behavioural or administrative reasons.

If a withdrawn participant agrees, any samples collected as part of this study prior to participant withdrawal will be retained, analysed and used by the study team for the purposes of this study. However, if a participant requests that their research sample is not tested and is destroyed, this will be performed and confirmed by the study team. Participants' samples for standard Cepheid testing will not be destroyed. These samples are needed for standard Trust Infection Prevention and Control testing and will therefore always be tested in line with Trust policy. Participants who withdraw from the study prior to sample collection, or who withdraw after sample collection and request their research sample is destroyed, will be replaced. A new unique study identifying number will be allocated to the replacement participant to prevent any confusion and ensure complete transparency regarding number of participants screened, recruited and withdrawn.

13.4 Randomisation

There are no treatment arms in this study and no randomisation procedure. All participants will be swabbed to provide samples that can be tested by the standard test procedures (Cepheid GeneXpert +/- second-line testing device as per Trust IPC policy) and the novel Logicore System testing device. In this way, each participant will act as their own control for comparison of results.

13.5 Schedule of Events

13.5.1 Per Participant Activities

Activity	At ED Visit
Review of PIS and signing of ICF/Assent form	Х
Signs and symptoms of acute respiratory tract infection	Х
Temperature	Х
Heart rate, respiratory rate, blood pressure and oxygen saturation	Х
Nasopharyngeal swabs x2 (simultaneously taken) for initial testing by standard Cepheid device and novel Logicore System device	Х
Additional nasopharyngeal swab for testing by second-line device*	Х
Assessment of acceptability (Likert-scale)	Х
Adverse event details	Х

^{*}Additional nasopharyngeal swab may or may not be required, depending on the results from the initial testing and depending on the clinical status of the participant according to Trust IPC policy.

13.5.2 General Study Activities

Activity	Undertaken By	Time Allocation
Informed Consent / Assent*	CI/RN	15 minutes
Study visit procedures and source documentation*	CI/RN	1 hour
Data input into eCRF*	CI/RN	30 minutes
Maintenance of ISF and Essential Documentation^	CI/RN	30 minutes
Query Resolution (following monitoring visit)^	CI/RN	30 minutes

^{*}per enrolled participant.

[^]per monitoring visit.

13.5.3 Study Sample Collection and Testing Process

Study staff undertaking the sample collection will wear appropriate personal protective equipment (PPE) for the risk exposure at all times, in line with CUH local guidelines for Infection Prevention and Control. To eliminate potential differences in the samples being tested, two nasopharyngeal swabs will be collected simultaneously. One swab will be tested by the gold standard Cepheid multiplex POC test (i.e. standard of care diagnostic testing as required by CUH Trust IPC policy) and the other with the novel Logicore System multiplex POC device. The Logicore System swab will be tested using a specific Logicore System buffer which will be provided for use in a closed vial by the Sponsor. The testing of each specimen (Cepheid or Logicore) must begin within 20 minutes from the time of swab collection, according to the specimen processing guidelines. There is no need to store the swabs/buffer solutions on ice. These can remain at ambient temperature for storage.

The Cepheid POCT is done in the laboratories above the ED. The Logicore System (i.e. the Analytical Module into which the Respiratory Pathogen Panel cartridge is loaded for analysis and the portable Operation Module with display screen, into which the cartridge details and participant anonymised details are input) will be located in a secure clinical area within the ED, with controlled access.

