5.0 PROTOCOL SYNOPSIS

C4d C	
Study Summary	
Protocol Title	Evaluation of Digital Microfluidic Molecular Point Of Care Testing for Respiratory Pathogens Diagnosis
Short Title	Study for Multiplex Assessment and Respiratory Test evaluation; SMART
Study Objectives	To evaluate the analytical performance, turnaround time, operability and acceptability of a novel multiplex respiratory pathogens point of care test device compared to currently available point of care testing.
Study Procedures	Participants will be swabbed to provide samples which will be analysed by standard testing and by the novel multiplex device. The procedures will take place in a single visit in the Emergency Department at Addenbrooke's Hospital in Cambridge. Additional relevant data will be collected from the participants' hospital medical records. No further participant involvement is required.
Study Sponsor	Logilet (UK) Ltd
Sponsor	[name] ([name])
Representative	Product Manager
Study Design	This is a prospective, single centre, single visit, diagnostic performance study. There is no therapeutic agent involved and therefore no randomisation into treatment arms. Two nasopharyngeal swabs will be taken simultaneously from each participant (one from either nostril) and used for Point Of Care Testing using the current gold standard and novel in vitro diagnostic devices. In this way, participants will act as their own controls for comparison of results. If the initial standard test is negative but the participant continues to exhibit clinical symptoms of respiratory infection, a further swab may be taken and tested as per Cambridge University Hospitals NHS Foundation Trust (CUH) policy with another standard device.
Investigational Medical Device	The Logicore System in vitro diagnostic device utilises digital microfluidics to rapidly test for the presence of 6 respiratory pathogens, namely SARS-CoV-2, Influenza A (FluA), Influenza

	Ţ
	B (FluB), Respiratory Syncytial Virus (RSV), Mycoplasma pneumoniae (MP) and human adenovirus (HAdV). The Logicore System produces results in approximately 63 minutes and is expected to feature improved sensitivity when compared to the current gold standard testing device.
Study Location	Cambridge University Hospitals NHS Foundation Trust (CUH)
	Emergency Department
	Addenbrooke's Hospital Cambridge Biomedical Campus
	[name]
	Cambridge
	[name]
Study Duration	When the sample size has been reached, or a maximum of four

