*Table showing impact of variable distribution of infection type on defining sample numbers (after CUH data)

Infection	Estimated Prevalence in	Number Needed for 19
	Winter Population	Positives
RSV	~15%	~127
Flu A	~10%	~190
Flu B	~5%	~380
SARS-CoV-2	~10%	~190

As the basis of this study is to determine sensitivity of the Logicore System testing device, rather than combined diagnostic performance across all four infections (rather than each one separately) then we need to apply this distribution imbalance to the way we calculate the minimum sample number to ensure at least achieving our sensitivity goal for each pathogen.

All eligible participants, i.e. those selected by the respiratory and inclusion criteria noted above with respiratory symptoms and a signed consent form, will be enrolled in the study. Using dual swabs, respiratory samples will be collected simultaneously for use in both new (Logicore System) and gold standard (Cepheid) tests to ensure comparability. This method will reduce the risk that differences in test outcomes are the result of inequitable sampling.

The aim also is to use the inclusion/exclusion criteria to recruit consecutive patients in the ED, suspected of the target condition to attempt to reduce spectrum bias. This real-world sample ensures external validity.

As this POCT occurs in a real time ITT setting, sample swabs will be handled consecutively within a few minutes to enter them into the POCT devices with no delay before and between test commencing. Both devices are expected to deliver a result with a similar elapsed time envelope. Hence commonly both tests will be running in parallel at any moment and model more closely the normal pathways of care in use.

This study is primarily aimed at validating the performance of a new POCT device (Logicore System) against an existing POCT device (Cepheid). This is the basis for this statistical plan rather than using a reference standard/composite diagnostic test e.g. PCR + Chest X-Ray.

Blinding the study will be difficult because of the situation of the study.

With regards to incorporation bias, the new test result will not influence the gold standard result.

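### Simultaneous swabbing controls timing only: the text does not assign nostril to device or record the side, so a swab difference tied to one device would count as device performance

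*Protocol*

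**What the plan says.** The Protocol Synopsis (5.0) describes the sampling: "Two nasopharyngeal swabs will be taken simultaneously from each participant (one from either nostril". Section 13.5.3 gives the purpose, "To eliminate potential differences in the samples being tested, two nasopharyngeal swabs will be collected simultaneously", and then the split: "One swab will be tested by the gold standard Cepheid multiplex POC test", with the other swab going to Logicore. Section 14.1 makes a weaker claim for the same procedure: "This method will reduce the risk that differences in test outcomes are the result of inequitable sampling".

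No section of the text links a nostril, a hand or an order to a device. Section 13.4 states: "There are no treatment arms in this study and no randomisation procedure". The reason given there is the lack of treatment arms, which does not bear on how swabs are assigned to devices. On concealment, 14.1 says only: "Blinding the study will be difficult because of the situation of the study". The data list in 11.0 records when the swabs were taken but not which nostril supplied which device.

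Handling is partly controlled. Section 13.5.3 requires: "The testing of each specimen (Cepheid or Logicore) must begin within 20 minutes from the time of swab collection". The two systems still differ in buffer and place: "The Cepheid POCT is done in the laboratories above the ED", while Logicore sits inside the ED.

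**The concern.** The paired design lets each participant act as their own control. That cancels differences between participants. It does not cancel differences between the two swabs from one participant unless swab and device are unlinked.

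The scoring rules have no category for a swab difference. Under 11.0, a Cepheid-positive, Logicore-negative pair is always a Logicore false negative. Under 14.5.1, McNemar's test per pathogen reads the imbalance of discordant pairs as a difference between tests, and a significant excess of Logicore positives may be taken as superior sensitivity. If the swab sent to one device tends to carry more material, that excess or deficit is credited to the device. Because side is neither assigned nor recorded, no later analysis could detect the imbalance or adjust for it. A later analysis plan therefore cannot repair it.

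**Working it through.** **The plan's own figures.** From 14.3.1, Z = 1.96, P = 0.95, d = 0.10:

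n = 1.96² × 0.95 × 0.05 / 0.10² = 18.25, rounded up to 19; 19 / 0.05 = 380; 380 + 20 = 400.

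These reproduce, and this point disputes none of them. With the winter prevalences in 14.1, 400 participants give 400 × 0.05 = 20 (Flu B), 400 × 0.10 = 40 (Flu A, SARS-CoV-2) and 400 × 0.15 = 60 (RSV) infected.

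**Illustration of the consequence.** The protocol gives no figure for a side or swab difference, so the pick-up values are assumptions:

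- The two devices are identical and each detects whenever its swab has picked up the pathogen.
- The better swab picks up with probability h = 0.95, the worse with probability w = 0.95, 0.90, 0.85 or 0.80, independently given infection.
- The test is the exact two-sided McNemar test at p < 0.05 among the infected. Section 14.5.1 describes the chi-squared form, whose rates would differ somewhat.

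Discordance probabilities per infected participant when the better swab always goes to one device:

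- b = h(1 − w), for w = 0.85: 0.95 × 0.15 = 0.1425
- c = w(1 − h), for w = 0.85: 0.85 × 0.05 = 0.0425
- expected net discordance = n(b − c) = 0.10n, that is 2, 4 and 6 pairs for n = 20, 40 and 60.

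If allocation is balanced (modelled as random, since infection should be unrelated to study number), both become (0.1425 + 0.0425) / 2 = 0.0925 and the expected net is zero.

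The number of discordant pairs D is binomial(n, b + c) and the split is binomial(D, b / (b + c)). Summing over outcomes where the exact test rejects gives the chance of false significance, shown as better swab always to one device / balanced:

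| Assumed pick-up | 20 infected | 40 infected | 60 infected |
|---|---|---|---|
| 0.95 and 0.95 | 0.0% / 0.0% | 0.4% / 0.4% | 1.1% / 1.1% |
| 0.95 and 0.90 | 0.5% / 0.1% | 4.4% / 1.1% | 9.4% / 1.9% |
| 0.95 and 0.85 | 2.9% / 0.4% | 18.0% / 1.7% | 33.0% / 2.3% |
| 0.95 and 0.80 | 9.2% / 0.7% | 39.3% / 2.1% | 62.3% / 2.6% |

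**Sensitivity as the protocol scores it** (Logicore positive among Cepheid positive), at 0.95 and 0.85:

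- better swab always to Cepheid: 0.85
- better swab always to Logicore: 0.95
- balanced: (0.95 × 0.85) / 0.90 = 0.897.

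Fixed allocation moves this estimate by 0.897 − 0.85 = 0.047 down or 0.95 − 0.897 = 0.053 up, about 0.05 either way. Balancing does not bring it to 1, although the devices are identical, because random swab-to-swab discordance remains.

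**The case against.** The strongest reply is that the harm is hypothetical. A habit such as always sending the left swab to Logicore biases nothing unless left and right differ on average across participants; differences that vary in direction from person to person add noise only. The protocol reports no such average difference. Under the smallest assumed gap (0.95 and 0.90), false significance exceeds the nominal 5% only with 60 infected. For the 5% pathogen that sets the sample size it is 2.9% even at 0.95 and 0.85. All of this stands, and it keeps the point at the level of a cheap improvement.

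A rule might also sit in Figure 1, the Instructions for Use or site training. The content of Figure 1 was not available for this check, so the finding is limited to the protocol's text. That text fixes no rule, and the data list in 11.0 omits the side. It is also fair that 14.1 claims only to reduce the risk, so the overstatement is confined to 13.5.3.

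Several stronger readings are tempting but unsupported:

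- A reader might infer that staff choose a device for each swab after inspecting both. The text does not say who decides, when, or on what basis; it only leaves that possible.
- A reader might say the primary result rests on discordant pairs alone. That is true of McNemar's test, but 14.5.1 also lists sensitivity, specificity, predictive values, likelihood ratios, accuracy and kappa, which use concordant cells too.
- A reader might expect a swab gap to bias sensitivity by its full size, and alternation to make the bias zero. Both hold for the difference in positive rates. Against Cepheid as reference, the allocation shift is about half the gap, and some shortfall remains after balancing.
- A reader might compare a yield difference with the quoted SARS-CoV-2 detection limits of 100 and 131 copies/mL. How many results would flip depends on how many samples lie near those limits, which the protocol does not give.

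**Conclusion.** The point holds in a limited form. Simultaneous collection cannot eliminate sample differences; it deals with timing. With no assignment rule in the text and no record of side, a swab difference linked to one device would be read as device performance and could not be examined afterwards. Bias in one direction needs two conditions that the protocol neither states nor rules out: side or swab choice is systematically tied to a device, and yield differs on average.

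The size is unknown. At the assumed 0.95 and 0.85, always giving one device the better swab raises false significance from 2.3% to 33.0% with 60 infected, from 1.7% to 18.0% with 40, and from 0.4% to 2.9% with 20. Sensitivity moves by about 0.05 from its balanced value of 0.897. These figures rest on identical devices, independent pick-up and the worst-case allocation. They show what the design leaves open, not what will happen.

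A reader might also infer that assigning nostrils would settle handling differences. It would not: buffer and location belong partly to each test system, and both tests already share the 20-minute start limit.

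**What to change.** In 13.5.3:

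1. Assign nostril to device by study number, read before swabbing. Odd numbers: left nostril to Logicore, right to Cepheid. Even numbers: the reverse.
2. Record in the eCRF the side actually used for each device.
3. Allow a recorded exception when the assigned allocation cannot be followed, so that such a case is not automatically a protocol deviation.
4. Replace *eliminate* with *reduce*, in line with 14.1.

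The study number is issued at enrolment (13.1) and consent precedes any study-specific activity (13.2), so the allocation is known in time. The cost is one extra eCRF field and a small step for staff. The 19, 380 and 400 in 14.3.1 do not change, and no extra swab or visit is needed. The change removes the systematic side or choice component only. Random swab-to-swab discordance and the buffer and location differences stay, and should be acknowledged when the results are interpreted.

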13.5.4 Participant Follow Up

Participants enrolled into the study will be considered to have completed their participation in the study once all the required swabs have been tested and results obtained. (This may simply be one set of 2 swabs, or one set of 2 swabs for initial Logicore System and Cepheid testing plus an additional single swab for second-line testing, if the initial Cepheid result was negative but the participant continues to exhibit clinical symptoms of respiratory infection and needs to be tested as per Trust IPC guideline). Any positive results will be communicated to the participant's medical care team and documented in their electronic medical records. No follow up is required for the study. Participants will continue to receive appropriate medical care outwith the study. This study has no bearing on the clinical management of the participants.

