8.2 Potential Benefits

The main potential benefits from using the Logicore System device compared to standard testing means are as follows:

- 1) The Logicore System can test for 6 different respiratory pathogens all at once, compared to 4 for the Cepheid GeneXpert device.
- 2) The Logicore System is expected to be more sensitive than the standard device. The minimum limit of pathogen detection is 100 copies/mL whereas the Cepheid GeneXpert device has a minimum limit of detection of 131 copies/mL for SARS-CoV-2³.
- 3) The Logicore System produces rapid results in around one hour, compared to the hour and a half using the UK HSA laboratory second-line test if the initial Cepheid test is negative but clinical symptoms persist.

There is no particular benefit to individual participants from taking part in the study. There are no payments to participants for taking part and the study has no bearing on the clinical care each participant receives. Once the swabs have been taken from participants, they will immediately return to standard clinical care without delay. However, if the Logicore System testing device detects a pathogen that is not identified by the Cepheid test, it may result in faster commencement of treatment with an appropriate therapeutic drug regime. Instigation of treatment will take place outwith the study and will be undertaken by the participant's ED care team. There is no Investigational Medicinal Product in the study itself.

Additionally, participants may experience a sense of altruism from taking part in a study aiming to reduce diagnostic time and spread of infection for future ED patients.

Any risks have been mitigated such that it is considered the benefits to those taking part in the study outweigh any potential risks.

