B. If the Cepheid and Logicore System results are positive for different pathogens, it is not possible to test the participant again as the result from the gold standard Cepheid test will be taken as correct and used to determine appropriate treatment. The participant would not have repeat testing according to standard care. If the Logicore System result is positive for one of the pathogens that Cepheid does not test for (i.e. *Mycoplasma pneumoniae* or human adenovirus), it will be taken to be a true positive result. If however, the Logicore System result is positive for a different pathogen that Cepheid does test for (i.e. Flu A, Flu B, RSV or SARS-CoV-2) but it is not the same pathogen that is positive according to the Cepheid result, the Logicore System result will be classed as a false positive.

C. If the Cepheid result is negative but the Logicore System result is positive, and the participant still exhibits clinical symptoms of respiratory infection requiring diagnostic testing as per CUH Trust Infection Prevention and Control Guideline, a second single swab will be taken from the participant and used for second-line testing as per the CUH Trust standard UK HSA laboratory respiratory virus PCR testing policy. The result from the second-line testing will then be compared to the initial Logicore System result. If the Logicore System result agrees with the second-line result, it will be classed as a true positive. If it does not match the pathogen from the second-line testing, the initial Logicore System result will be classed as a false positive.

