14.0 STATISTICAL ANALYSIS PLAN

14.1 Rationale

According to the Office of National Statistics report on the results of the 2021 Census⁷, the population of Cambridge is approximately 146,000 people. Of this population, around 75% classed their ethnicity as White (comprising the following categories: British, Irish, Roma, Gypsy or Irish Traveller, or Other) and around 15% are children aged 15 years or less. For this clinical study, it is expected approximately 20% of participants will be less than 16 years of age, and the majority of participants will be white Caucasian, providing a casemix with external validity in line with the demographics of the catchment area.

This prospective paired diagnostic accuracy and economic evaluation study is designed to assess the clinical performance and potential health system impact of a new molecular Point Of Care Test for respiratory infections in the Emergency Department (ED) setting. The new Logicore System testing device detects six key respiratory pathogens including four infections currently targeted by the current gold standard test (Cepheid); Influenza A (Flu A), Influenza B (Flu B), Respiratory Syncytial Virus (RSV) and SARS-CoV-2. The Logicore System device detects two additional pathogens not included in the established POCT; *Mycoplasma pneumoniae* (MP) and human adenovirus (HAdV).

During the winter season planned for this study, the overall positivity of the current POCT for respiratory disease is estimated at 30-50% of those selected by the respiratory criteria for the standard test (CUH personal communication). However, it is recognised that infections do not distribute evenly by age, or season, or time of the season. For example, RSV is more common in the very young or elderly and has peaks later in the winter months. Thus, the statistical approach to assessment requires us to estimate how many true positives per infection type* might be expected to achieve a sensitivity of 95% with a 10% margin of error, not just overall.

Also, during the winter season, disease type incidence will occur in runs and hence it is possible to inadvertently populate the whole study with one type of infection.

Logically our total sample size will need to be calculated on the lowest prevalence infection. As this is planned as an Intention To Treat study (ITT), i.e. including clinical benefits, then 10-15% extra samples would provide a reasonable margin of samples to allow for withdrawals and invalid samples.

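### Logicore-only positives reach the care team although the protocol denies any influence on care, and the within-trial cost comparison needs two courses of care from patients who each have one

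*Protocol*

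**What the plan says.** **Release of results.** Protocol section 13.5.4 states: "Any positive results will be communicated to the participant's medical care team and documented in their electronic medical records". The same paragraph ends: "This study has no bearing on the clinical management of the participants". Section 8.2 says likewise that "the study has no bearing on the clinical care each participant receives", and then allows that if Logicore finds a pathogen Cepheid misses, "it may result in faster commencement of treatment with an appropriate therapeutic drug regime".

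**Discordant results.** Under rule B in section 11.0, when the devices are positive for different pathogens, "the result from the gold standard Cepheid test will be taken as correct and used to determine appropriate treatment". Under rule C, a patient who is Cepheid-negative and Logicore-positive has a second swab for second-line testing only on a further condition: "and the participant still exhibits clinical symptoms of respiratory infection requiring diagnostic testing as per CUH Trust Infection Prevention and Control Guideline".

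**Design.** Section 13.4 has no arms and no randomisation; "each participant will act as their own control for comparison of results".

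**Economic analysis.** Section 14.2.4 commits to a within-trial cost-effectiveness analysis that uses trial data to compare diagnostic pathways. Section 14.3.4 takes as its population those who are negative on the standard test, positive on the new one and still symptomatic. The outcomes it suggests include length of stay, complications and time to treatment. Its worked example (£500 saving, SD £1000) gives 31.4, rounded to 32 per group. It then expects 20 to 25 patients per extra infection and regards that as sufficient. Section 14.5.4 offers either a cost-effectiveness analysis or a decision-analytic model, and considers a simple decision tree suitable.

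**The concern.** There are two linked problems.

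First, the protocol releases the result of the device under evaluation and at the same time denies, without qualification, that the study affects management. Staff are not told whether they may act on a Logicore-only positive before it has been confirmed.

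Second, the economic plan rests on the patients for whom this is left open. Pairing supplies two test results per person but only one length of stay, one treatment start and one cost. If the Logicore positive reaches clinicians early and they act on it, the observed course is the new pathway. Using it to represent current care would then make current care look faster than it is. If clinicians do not act until the second-line result arrives, the earlier treatment credited to the new pathway never appears in the data. Either way, a comparison of observed outcomes in these patients cannot show what the new pathway saves.

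**Working it through.** **1. Does the release rule cover Logicore-only positives?** The sentence before it in section 13.5.4 lists the Logicore, Cepheid and second-line swabs, so any positive result naturally includes Logicore. Rule B restricts treatment decisions to Cepheid only when both devices are positive for different pathogens. Rule C uses the second-line result to classify the Logicore result as true or false positive, and does not make it a condition of release. Nothing else in the protocol holds back a Cepheid-negative, Logicore-positive result.

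**2. What can be observed in a Cepheid-negative, Logicore-positive patient?**

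| Use of the Logicore positive | Downstream course observed | Course not observed |
|---|---|---|
| Acted on before the second-line result | New pathway | Current pathway |
| Not acted on until the second-line result | Current pathway | New pathway |

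Test results on both routes can be seen within a patient. Treatment time, length of stay and cost can be seen on one route only.

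**3. Reproducing the example in section 14.3.4.** Inputs: difference £500, SD £1000. Alpha and power are not stated; I assume two-sided 0.05 and 80%.

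n = ((1.960 + 0.842) × 1000/500)² = (2.802 × 2)² = 31.4, rounded up to 32.

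This matches the protocol's figure. It is the one-sample or paired form, so it needs each patient's cost difference between the two pathways. Step 2 shows that this difference is not observable.

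**4. If the words per group are taken literally.** Two independent groups need twice the variance term:

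n per group = 2 × 31.4 = 62.8, rounded up to 63, or 126 in all.

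With 32 in each of two groups, power would be about 52%.

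**5. Patients available.** The stated maximum share is 5%, and 0.05 × 400 = 20. The upper figure of 25 would be 25/400 = 6.25%, above that maximum. Reaching 32 at 5% would take 32/0.05 = 640 participants.

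| Patients | Power, paired form | Power, that many in each of two groups |
|---|---|---|
| 20 | 61% | 35% |
| 25 | 71% | 42% |
| 32 | 81% | 52% |

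The protocol attaches 20 to 25 to each extra infection. Pooling two infections would give 40 to 50, which passes 32 under the paired form (power 89% to 94%). They would still all lie on a single realised pathway, and would still fall short of 126.

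**6. Data items.** The collection list in section 11.0 has the Cepheid and Logicore result times. It does not list second-line result time, treatment start, length of stay, or whether treatment or isolation followed the Logicore result.

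**The case against.** **The denial can be read more mildly.** Section 8.2 qualifies it at once and places treatment outside the study with the emergency department team, so it may mean only that the study does not direct care. That is a fair reading of the intent. The words are still wrong as they stand, because the study supplies the result that may prompt treatment.

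**The decision tree is already there.** Section 14.5.4 offers one, and some of its inputs, such as utilities, must come from outside because section 11.0 collects none. The source of model inputs is also ordinary detail for a later plan. This softens the point considerably. But the tree is only an alternative, while sections 14.2.4 and 14.3.4 fix trial data and real patients as the basis. That commitment needs correcting.

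**Hospital records may fill the gaps.** The synopsis allows further data from records, so some timings may be recoverable. Whether an action followed the Logicore result is harder to reconstruct.

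**The £500 case is only an example.** True. The 400 comes from section 14.3.1 and is not called into question here.

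**Stronger readings that the documents do not support:**
- A reader might infer that nothing in the study informs the current pathway. Sections 7.1 and 13.5.4 tie second-line testing to a negative Cepheid result with continuing symptoms, so Cepheid-negative, Logicore-negative participants may also have it. They can inform reflex-test cost, delay and isolation, though they are a selected group.
- A reader might double 32 to get a requirement of 64. That fits neither form: it is 32 in total if paired, or 63 per group if independent.
- A reader might take section 14.2.4 to name the Logicore-positive population. It refers only to patients negative on the standard test with ongoing symptoms; section 14.3.4 adds the Logicore-positive condition.
- A reader might rely on section 14.1, "As this is planned as an Intention To Treat study (ITT), i.e. including clinical benefits". That sentence supports a sample-size margin and says nothing about release of results.

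**Conclusion.** The point holds and should be fixed, within limits. The unqualified statements in sections 8.2 and 13.5.4 conflict with the release of any positive result and with section 8.2's own concession. The comparison in sections 14.2.4 and 14.3.4 cannot be made from observed outcomes, because each discordant patient has one course of care and there is no comparison arm.

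The section 14.3.4 example does not support its conclusion that the expected numbers are enough. The stated maximum yields 20 patients (20 to 25 per infection in the protocol's words), against 32 under a paired formula whose data cannot be observed, or 63 per group for independent groups. These figures assume two-sided alpha 0.05 and 80% power.

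The direction of bias depends on when the result is released and whether clinicians act on it. Its size in days or pounds cannot be derived from the protocol. Paired accuracy and turnaround time are unaffected.

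**What to change.** 1. **Sections 8.2 and 13.5.4.** Qualify the two statements about care: the study does not direct treatment, but a reported Logicore positive may inform it. State whether clinicians may act on a Logicore-only positive before second-line confirmation.
2. **Sections 14.2.4 and 14.3.4.** Replace the within-trial comparison of observed outcomes with the section 14.5.4 decision tree. Do not use the discordant patients' observed length of stay, time to treatment or cost as the current pathway. Take current-pathway inputs from patients managed without a Logicore positive: routine Trust data and, with caution about selection, Cepheid-negative, Logicore-negative participants sent for second-line testing. Restate or remove the 32 per group and the claim that the expected numbers suffice.
3. **Section 11.0 data list.** Add second-line result time, treatment start time, and whether treatment or isolation followed the Logicore result. Do this before recruitment, since these may not be recoverable later.

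The cost is a few sentences and three record items. The economic comparison becomes modelled rather than observed and needs some external inputs. Sample size, swabbing and testing do not change.
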